 - During the hospitalization (from day 2 to day 6) the panel of the blood tests could be modified.
- note 3: the assessment of liver function includes: ALT, AST ALP, bilirubin and total protein, gamma-GT,.

 During the hospitalization (from day 2 to day 6) the panel of the liver function could be modified.

- note 4: viral titres include: Hepatitis B and C. Tests to be performed only if not yet available within the medical history of the patient or if the previous results available have to be confirmed. HIV test is performed according to Principal Investigator or his delegates decision.
- note 5: hematology, the assessment of liver function, the determination of the viral titres and the pregnancy test, if applicable, will be evaluated by the Principal Investigator (PI) and/or his delegates and recorded first in the patient's medical record and then in the eCRF. The Principal Investigator and/or his delegates will check the laboratory test results vs. the inclusion/exclusion criteria. In case any result shows an out of range parameter judged to have an impact on the Inclusion/exclusion criteria, this will be repeated before the confirmation for randomization.
- note 6: randomization will be performed by an independent statistician who will maintain it during the entire period of the study.
- note 7: the Principal Investigator and/or his delegates will record, first in the patient's medical record and then in the eCRF, the following information: source of bleeding, bleeding severity using "oozing" or "moderate", approximate area of bleeding.
- note 8: the Principal Investigator and/or his delegates will record, first in the patient's medical record and then in the eCRF, the following information: hepatic parenchyma characteristics, intraoperative measurement of total volume of transfused blood products, duration of the surgery, type of the hepatic resection, the estimated intraoperative blood loss, the use of Pringle's maneuver.
- note 9: the Principal Investigator and/or his delegates will record, first in the patient's medical record and then in the eCRF, the output (in ml) and the characteristics of the perihepatic drains (drain pigmentation, i.e.biliary bloody clear). These information will be recorded by the Principal Investigator and/or his delegates from day 1 after surgery to the End of Study Visit if the drainage is still in place.

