 volume of transfused blood products, duration of the surgery, type of hepatic resection, the estimated
 intraoperative blood loss and the use of Pringle's maneuver) Concomitant medications recordings
- Adverse event (intraoperative and not-intraoperative) assessment and recording

The patients randomized to Common Surgical Techniques (CST) will be treated conventionally while the patients randomized to experimental technique (CST + Hemopatch) will be treated conventionally with the adjunct of Hemopatch.

For patients included in ARM B Hemopatch is applied upon the verification made by the surgeon of the presence of an appropriate target bleeding (oozing or moderate) site in the hepatic parenchyma. At the time point of application a stopwatch starts simultaneously (time zero). Time to hemostasis is defined as the time required to obtain successful haemostasis in a single bleeding site. This time will be recorded by the operator delegated by the Principal Investigator and according to the surgeon's observation. At 3 minutes the inspection will be made and, if haemostasis is not

achieved, the treatment is considered failed and the Principal Investigator and/or his delegates is allowed to use additional haemostatic measures (including other topical haemostatic agents).

The time to haemostasis will be recorded before in the patient's medical record and then in the eCRF. The bleeding site will be observed for 1 additional minute (after the first 3 minutes) at the end of the haemostatic procedure and at the end of the surgery, in order to confirm the achievement of haemostasis. At the end of surgery at least one perihepatic Jackson-Pratt drain will be left near the site of resection.

Patients allocated to ARM A, will undergo the conventional hemostatic procedures and therefore also these patients will end up with a perihepatic Jackson-Pratt drain, which will be left near the site of resection.

Visit 4 (+1 day after Surgery): Day 2

- Hematology examinations, which includes: glucose, urea nitrogen, creatinine, sodium, potassium, calcium, total
 cholesterol, HDL and LDL, triglyceride, alkaline phosphatase, LDH, complete blood cell counts with differential and
 platelet counts, APTT, PT, INR, fibrinogen, VES, PCR
- · Liver function test examinations, which include: ALT, AST, ALP, bilirubin and total protein, gamma-GT
- Output (in ml) and characteristics of the perihepatic drains (drain pigmentation, i.e. biliary bloody clear)

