6.3 Withdrawal procedures

Patients have the right to withdraw from the trial on their request or at the discretion of the Principal Investigator and or his delegates.

The discontinuation from the study is foreseen in the following conditions:

- ✓ patient's request (also not motivated);
- ✓ principal investigator's decision (motivated) if considered as necessary, in own judgment, for the interest of the patient;
- ✓ occurrence of new diseases clinically relevant, not related to the study treatment;
- ✓ occurrence of particularly important adverse reactions;
- ✓ occurrence, in the course of the study, of one or more of the situations listed in the "exclusion criteria".

Patients withdrawn because of Hemopatch's failure, should be monitored for safety until the end of the study (please refer to the section 9.1).

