7.1.1 Application of Hemopatch

The investigator will select the appropriate size of the pad so that it overlaps the margins of the bleeding surface by about 1 cm. The pad may be cut to the desired size and shape. Dry gloves and surgical instruments (forceps, scissors) should be used to handle, cut and apply Hemopatch. Multiple pads may be used for larger bleeding surfaces. The investigator will apply the dry Hemopatch with the non-marked white surface contacting the bleeding area. A dry gauze or patty will be used and will be hold in place with gentle, uniform pressure over the entire pad surface for 2 minutes. When applying Hemopatch, the investigator should minimize contact with bloody surgical instruments, gauzes or gloves due to the affinity of collagen to blood. After 2 minutes, the investigator should gently remove the gauze or patty from the pad; gentle irrigation may also help in removing the gauze or patty without dislodging Hemopatch from the bleeding site. If the bleeding has not been satisfactorily controlled, Hemopatch can be removed, without tissue damage, up to 3 minutes from the time of the initial tissue contact. The investigator should not try to forcefully remove the pad.

The target bleeding site is defined as a bleeding site that, after 30 seconds of firm manual compression, has persistent bleeding requiring immediate attention. The investigator, an experienced hepatic surgeon, will define the bleeding source (arterial, venous, capillary), bleeding severity (oozing, middle or spurting) and the approximate area of bleeding site (cm², mean).

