- within 10 calendar days by occurrence for incidents;
- > within 30 calendar days by occurrence for near incidents.

The form provided in Appendix I (in Italian) is to be used to report incidents and near incidents. It must be filled in with all the available information, dated and signed.

Upon request by the Regulatory Authorities, the Investigator must complete his report with all available follow-up information.

Reports on complaints must be transmitted to the manufacturer/ authorized representative/distributor within 30 calendar days by event occurrence.

The MD involved in the notified incident/near incident, if still available, must be kept at the Pharmacy of FPG and, unless otherwise specified by Ministero della Salute, delivered to the concerned company within 10 calendar days from the submission date of relevant incident or within 30 calendar days from the submission date of relevant near incident.

Transfer Of Regulatory Obligations

The regulatory obligations are delegated by the Investigator to the Clinical Trial Center – FPG, ACRO Unit. If the Investigator becomes aware of an incident/near incident/complaint as defined above, he must immediately report (not later than 24 hours from the knowledge) to the Clinical Trial Center – FPG by filling in the dedicated form (Appendix I). The form should be compiled in Italian. The reference contacts are reported in the table hereafter.

Clinical Trial Center				
Fondazione Policlinico Universitario A. Gemelli Università Cattolica del Sacro Cuore				
[name]				
FORM Transmission (incident/near				
incident/complaint)				
e-mail	[contact]			
Fax number (to be used just in case of				
electronic mail crash)	[name]			
Contact Person	[name]			
[contact]			
[contact]			
e-mail	[contact]			

Safety Follow-up

The safety information will be recorded starting from the date of the Informed Consent signature by the patient and will end-up at the End of Study Visit. This approach will apply also to those patients who were dropped out from the study because of failure of Hemopatch effect (and therefore treated with a rescue therapy), but who were left Hemoptach on the resection site because of difficulty in removing it. Those patients will be requested to return to the site to perform regularly from Visit 4 to Visit 8.

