11.5 Efficacy analyses

Responder definition

A patient is defined as "Responder" if he/she achieves hemostasis after 3 min. Time to haemostasis is defined as the time required to obtain successful haemostasis in a single bleeding site. At 3 min, the inspection will be made and, if haemostasis is not achieved, the treatment is considered failed and the patient will be defined as "Non-Responder". A patient assigned to the experimental arm (Hemopatch) for whom was not possible, for any reason, to proceed with the assigned treatment (i.e. has to be treated with the standard care) will be considered as "Randomization failure" and excluded from the ITT population.

In accordance with the primary objective of the study, the proportion of responder patients measured at treatment end (i.e. visit 3) will be the primary endpoint.

The treatment comparison will be performed by a χ^2 test.

The test will be two-sided and conducted at the standard 0.05 significance level

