11.6 Safety analyses

The Safety population will be used to evaluate safety and tolerability data.

Physical examinations, vital signs, laboratory tests, adverse events and concomitant medications will be considered for the safety and tolerability evaluation.

Categorical variables (physical examination normality, etc.) will be analyzed with shift tables (baseline vs. last visit), while continuous variables (laboratory parameters, vital signs, etc.) by descriptive summaries.

Laboratory data will also be analysed with shift tables (baseline vs. last visit), considering each value as being normal/abnormal with respect to the appropriate normal ranges.

Baseline conditions and adverse events will be coded using the MedDRA dictionary. All the data related to the baseline conditions and adverse events will be listed by patient. Descriptive statistics will be performed classifying the events by system organ class and preferred term; they will also be classified by seriousness and relationship with the study treatment.

Prior and concomitant medications will be summarized using the WHO coding system.

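### Sections 8.1 and 6.3 assume that Arm B patients can leave the study for Hemopatch failure, which 5.2 and 11.5 treat as an outcome; if followed, a few Arm B failures could lack later drain data, with no counterpart in Arm A

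*Protocol*

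**What the plan says.** **Failure as an outcome.** Section 11.5 says that without haemostasis at the 3-minute inspection "the treatment is considered failed and the patient will be defined as" a Non-Responder. Section 5.2 (Visit 3) adds that the investigator "is allowed to use additional haemostatic measures (including other topical haemostatic agents"). Neither section takes the patient out of the study. Section 6.3 lists five conditions for discontinuation, and treatment failure is not one of them. The synopsis plans eight visits for patients without distinguishing arm or response, and 5.2 schedules the 30-day visit for each patient.

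**Failure as a reason for leaving.** Section 8.1 (Safety Follow-up) refers to patients who were "dropped out from the study because of failure of Hemopatch effect (and therefore treated with a rescue therapy"). Where the patch stayed on the resection site because it was hard to remove, it continues: "Those patients will be requested to return to the site to perform regularly from Visit 4 to Visit 8". The closing sentence of 6.3 says that patients withdrawn because of Hemopatch's "failure, should be monitored for safety until the end of the study (please refer to the section 9.1"). Section 9.1 covers eCRF documentation and holds no follow-up rule.

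**Patch removal.** Section 7.1.1 foresees it: "If the bleeding has not been satisfactorily controlled, Hemopatch can be removed, without tissue damage, up to 3 minutes" from first tissue contact.

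**Arm A.** No text speaks of dropping or recalling Arm A patients because haemostasis failed. The general 6.3 list applies to both arms.

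**The concern.** A site cannot tell from these sections whether a rescued Arm B patient stays in the study. If 8.1 and 6.3 are taken at their word, such a patient may leave. If the patch was removed, no sentence then asks for Visits 4 to 8. Safety monitoring under 6.3 does not replace those visits, because 11.6 defines safety narrowly: "Physical examinations, vital signs, laboratory tests, adverse events and concomitant medications will be considered for the safety and tolerability evaluation". Drain output and drain removal are not on that list.

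Total drainage volume, timing of drain removal and bile leaks are secondary endpoints (4.1), and shortening drain use is a secondary objective (3.2). A failed Arm B patient who received the patch belongs to the ITT population of 11.2, so the efficacy analysis needs these data. Any loss would be tied to outcome and confined to one arm. If failures do worse after surgery, the comparison would tilt toward Hemopatch.

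**Working it through.** **1. The sections side by side**

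| Section | A failed Arm B patient... |
|---|---|
| 5.2, Visit 3 | may be rescued; no withdrawal stated |
| 11.5 | is a Non-Responder; no withdrawal stated |
| 6.3, list | is not covered by a listed condition as such |
| 6.3, last sentence | may have been withdrawn; safety monitoring to study end; pointer to 9.1 |
| 8.1 | may have dropped out; Visits 4 to 8 requested if the patch was left in place |
| Synopsis, 5.1, 5.2 | has the same visits as everyone else |

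The last row is the default. The 6.3 closing sentence and 8.1 presuppose departures that the other sections do not provide for.

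**2. Which data are exposed**

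- Drain output is scheduled at Visits 4 to 8; note 9 of the flow-chart has it recorded "from day 1 after surgery to the End of Study Visit if the drainage is still in place". Drain bilirubin and ultrasound are at Visit 5, and drain removal at Visits 6 and 7.
- Days 2 to 6 (Visits 4 to 6) are described as hospitalisation, and note 9 sends drain output to the medical record first. In-hospital drain output, an in-hospital removal date and length of stay should therefore mostly be recoverable.
- Two items are less secure for a patient regarded as out of the study: the protocol-scheduled Visit 5 bilirubin and ultrasound, and the output and removal of drains still in place after discharge.

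**3. The plan's own figures**

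Inputs from 11.1 and 11.5: 66% versus 34%, 90% power, two-sided 5%, 49 per arm. With pooled variance under the null and no continuity correction:

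n = [1.960 × √(2 × 0.5 × 0.5) + 1.282 × √(0.66 × 0.34 + 0.34 × 0.66)]² / 0.32² = 49.2, so 50 per arm. Power at 49 per arm is 89.9%. The planned 98 reproduces to within 2 patients and is not in dispute.

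Expected failures at 3 minutes:

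- Arm B: 49 × 0.34 = 16.7
- Arm A: 49 × 0.66 = 32.3

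**4. Size of a possible bias**

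Two quantities are not in the protocol and are assumed over a range:

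- s: the share of Arm B failures who are dropped, have the patch removed and contribute no data on the endpoint.
- d: how much worse, in SD, the 34% hardest bleeders do on an outcome such as days to drain removal.

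Further assumptions: the patch has no postoperative effect, the same 34% exist in both arms, and Arm A keeps all of them.

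- Lost from Arm B = 16.66 × s
- Hard bleeders remaining in Arm B, h = 0.34(1 − s) / (1 − 0.34s)
- Spurious difference toward Hemopatch = (0.34 − h) × d

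| s | Lost | Left in Arm B | h | Shift, d = 1 | Shift, d = 0.5 |
|---|---|---|---|---|---|
| 0 | 0 | 49.0 | 0.340 | 0 | 0 |
| 0.10 | 1.7 | 47.3 | 0.317 | 0.023 SD | 0.012 SD |
| 0.25 | 4.2 | 44.8 | 0.279 | 0.061 SD | 0.031 SD |
| 0.50 | 8.3 | 40.7 | 0.205 | 0.135 SD | 0.068 SD |
| 1 | 16.7 | 32.3 | 0 | 0.340 SD | 0.170 SD |

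For a shift of 0.1 SD at d = 1, h must be 0.24, so s = 0.10 / (0.34 − 0.24 × 0.34) = 0.387, or about 6.4 of the 17 failures. For scale, the standard error of a standardised difference with 49 per arm is about √(2/49) = 0.20 SD. The table assumes that the endpoint is wholly missing for lost patients, so it overstates the shift wherever the medical record fills part of the gap.

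**The case against.** The case for leaving the text alone has several sound parts.

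- **8.1 is additive.** It stands in the vigilance chapter and extends safety recording to patients with a retained patch, for a device reason: resorption takes 6 to 8 weeks (7.1). It does not release the other failures, and 6.3 asks for safety monitoring of all of them. This stands for safety data. It does not supply drain data.
- **The general schedule covers everyone.** The synopsis and 5.2 exempt neither failures nor an arm, so the natural default is that a Non-Responder continues. This stands, and it means that the loss is possible rather than prescribed. It does not resolve the conflict, because 8.1 still writes a special recall for one subgroup of drop-outs.
- **Withdrawal for failure may simply mean the investigator's motivated decision.** Section 6.3 allows that in either arm. The reading is possible, but only Arm B has failure-specific wording.
- **Few patients would be affected.** Removal is allowed up to 3 minutes, with pressure held for the first 2, and failure is declared at 3. The window closes as failure is declared. This stands.
- **The endpoints are exploratory**, and 11.5 specifies a test only for the primary endpoint. This stands.

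A reader might infer that the protocol orders all of the roughly 17 expected Arm B failures out, with length of stay and all drain data lost. The documents do not support that. No sentence orders withdrawal, patients with a retained patch are recalled, and the in-hospital data go to the medical record. The row s = 1 is an arithmetic upper bound.

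**Conclusion.** The inconsistency is real and lies in conduct rules that the protocol itself fixes. Sections 8.1 and 6.3 presuppose departures for Hemopatch failure that 5.2, 11.5, the 6.3 list and the visit schedule do not provide for. The two sections differ on who is followed and how, the 6.3 pointer to 9.1 is wrong, and Arm A has no counterpart.

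The consequence is limited. Some Arm B failures, probably few, could lack the Visit 5 drain bilirubin and ultrasound and the post-discharge drain output and removal data. With s between 0.1 and 0.25 and d = 1, the shift toward Hemopatch is 0.02 to 0.06 SD, or 0.1 to 0.3 of a standard error. It reaches 0.1 SD only if 6 to 7 of the 17 failures are lost and failures are a full SD worse. Both s and d are assumptions.

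The primary endpoint is settled at Visit 3 and is unaffected. Adverse events, including a clinically evident bile leak, and mortality should be captured under 6.3. The point is worth correcting because the possible loss is related to outcome, falls on one arm, and is nearly free to prevent.

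**What to change.** 1. State in 6.3 and 8.1 that failure at 3 minutes, or use of rescue, is not a reason for withdrawal in either arm.
2. Delete from 8.1 the wording on dropping out for failure and the restriction to patients whose patch was left in place. Align the last sentence of 6.3, and change its pointer from 9.1 to 8.1.
3. Have all patients in either arm who undergo resection and are treated complete Visits 4 to 8 with the secondary endpoints recorded, unless consent is withdrawn. The rule need not cover every randomised patient, since some may prove ineligible for resection during surgery (exclusion criterion 9).

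The cost is protocol wording and follow-up visits for a small number of additional Arm B patients (about 17 at the very most), who are expected to be in hospital for the early visits anyway. Sample size and primary analysis do not change.

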9. QUALITY CONTROL PROCEDURES

9.1 Data documentation and reporting

Electronic case report forms (eCRFs) will be used for study documentation. eCRF entries will be transcribed from source documents. Assessments for which source documents are usually available include laboratory data, medical history, physical examination, etc.. The Principal Investigator and/or his delegates should place all source documents in the patient's medical record.

Details of the eCRF completion will be explained to the Principal Investigator and/or his delegates during the Site Initiation Visit (SIV) by the statistician. All entries in the eCRF must be made in English language. The Principal Investigator and/or his delegates must give a reasonable explanation for all missing data. Each delegate of the clinical staff needs to register for eCRF entries with an individual user name and password. The eCRFs must be updated after each visit provided by the clinical study. If corrections are made to entries in the eCRF by the Principal Investigator or his delegates, the automated audit trail will keep track of all changes.

9.2 Study monitoring

Accredited study monitors appointed by the Clinical Trial Center (CTC) of the Fondazione Policlinico Universitario A. Gemelli will carry out the monitoring of the clinical study. The eCRF will be reviewed on site and checks will be made against source documents. The Principal Investigator and/or his delegates must ensure that the medical records will be available for direct verification of source data. To this end, the Principal Investigator or his delegates agree to allow regular visits (frequency depending on enrollment) by the study monitors and to ensure they have adequate access to study personnel and documents.

9.3 Inspections

The PI and/or his delegates must allow the Regulatory Authority to conduct Inspections.

The Inspection conducted by the Regulatory Authority consists of an official review of the documents, facilities, records and any other resource considered by the Authority to be connected with the study.

10. DATA MANAGEMENT

The data collection will be carried out at site. The data will be entered by the Investigator or a designee in a web-based Data Base provided by CMV-Stat. The electronic system will include the data entry pages prepared on the basis of the study flow-chart (section 5.1).

The data cleaning will be performed by CMV-Stat Data Management team who will provide the Investigator with the list of the detected inconsistencies on each group of data analyzed. The validation of the inconsistencies (change or acceptance) will be made by the Investigator. Before the data freezing, CMV-Stat will code the medical terms according to the following dictionaries (a Validation Coding Report will be prepared by CMV-Stat Biologist in charge and approved by the Sponsor or his delegates):

- MedDRA for the pathologies and the Adverse Events
- WHO-ATC for the drugs

At the end of the study, CMV-Stat will be in charge of the Data Base freezing. The Data Manager in charge will provide the Biostatistics Unit with the cleaned Data Base for the Statistical Analyses.

